Structured Clinical Interview for DSM-IV-TR: Anti-Social Personality Disorder. The SCID (First, Spitzer, Gibbon, & Williams, 1998) provides diagnoses of Axis I mental disorders and Axis II personality disorders consistent with the Diagnostic and Statistical Manual of Mental Disorders, text revision (DSM-IV-TR) (American Psychiatric Association, 2000). Reliability

(ranging from .72 to .97) and validity (ranging from .75 to .95) have been reported in several studies (Babor, Del Boca, & McRee, 1997; Kranzler et al., 1996). For this study, only the Axis II section on Anti-Social Personality Disorder will be administered at baseline. Interviewers will receive training in the use of the SCID (see below under *Interviewer Training*).

Brief Symptom Inventory (BSI). The BSI (Derogatis & Melisaratos, 1983) is a 53-item questionnaire derived from the Symptom Checklist-90 that assesses nine medical and psychological symptom dimensions: somatization, obsession-compulsion, interpersonal sensitivity, depression, anxiety, hostility, phobic anxiety, paranoid ideation, and psychoticism, which can be combined to form a Global Severity Index. Cronbach alpha is .71 to .85 and test-retest reliability is .68 to .91 across the dimensions.

Barratt Impulsiveness Scale Version 11 (BIS-11). Because impulsivity has been found to be a significant moderator of relapse, particularly within contingency management studies (Dawe, Gullo, & Loxton, 2004; Reily, Roll, & Downey, 2000), we will administer the Barratt Impulsiveness Scale at baseline. This scale is a 30-item self-report measure of three aspects of impulsiveness: attention impulsiveness, motor impulsiveness, and non-planning impulsiveness. It has excellent internal reliability and clinical utility for measuring impulsiveness in inmate populations (Patton, Stanford, & Barratt, 1995).

5. Treatment

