For the primary outcomes of admission and attendance, there will be no attrition since these outcomes will be based on program records. For the Admission Phase, the target sample size of 250 will allow detection of medium effects in comparisons between groups on the percentage of clients who enroll in treatment at Walden House, with $\alpha = .05$ (two-tailed) and power .80. For the Attendance Phase, with retention as the outcome, the sample size of 200 will allow detection of similar effects between groups. For the 12-month outcomes, the effect size will be smaller, possibly around $d = 0.30$, based on a previous meta-analysis of drug abuse treatment generally (Prendergast, Podus, Chang, & Urada, 2002). Here, where the analysis will be based on the follow-up interview sample in the Attendance Phase (~170), power is likely to be about .75. For arrest and reincarceration, where there will be no attrition, power will be at least .80. Inclusion of covariates may increase power somewhat (Tabachnick & Fidell, 1996).

PRELIMINARY AND DESCRIPTIVE ANALYSES

As noted above, faxable forms will allow many of the instruments to be quickly entered and checked, making it possible to periodically examine the data. Descriptive statistics on variables of interest will include percentages, means, correlations, measures of variance, and distribution characteristics, as appropriate to the measurement level of selected variables. Frequency tables will be used to examine cell sizes for categorical variables and non-normality for continuous variables. Where categorical variables have small cell sizes, we will collapse the categories where possible to create cells of sufficient size. Where variables are non-normally distributed, we will transform the variable if possible or use a non-parametric approach. If outliers are present, they may be recoded or omitted. Descriptive analyses will provide statistics on treatment-related variables, including percentage of sessions attended, number of weeks attended, value of vouchers earned, and items for which vouchers were redeemed.

DESIGN ANALYSES

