Treatment retention. Retention will be measured as both a categorical and a continuous variable. Treatment completion will be coded as yes or no and will be defined as attending the Walden House program for 26 weeks or leaving under favorable circumstances (e.g., clinically approved early discharge, transfer to another program, moving to another county). Treatment retention will be measured as the number of days of attendance at Walden House (up to a maximum of 26 weeks or 180 days).

Substance use. For the follow-up period, recent substance use will be defined as either self-report of use or a positive drug test result. Recency and frequency measures of substance use from the CJ-DATS form will also be used.

Criminal justice involvement and criminal activity. State criminal justice records will be used to determine the number and type of rearrest or reincarceration and the number and type of case dispositions (probation, jail, prison, technical violation, or new conviction) over the 18-month period following release to parole (covering the six-month intervention period and the 12-month follow-up period). These measures will also be considered as binary variables (i.e., any arrest during the specified period vs. none, reincarceration vs. none). Since criminal justice history variables are event based with specific dates, we will also be able to calculate time to rearrest or reincarceration. On the basis of self-report responses on the CJ-DATS form, crime outcomes will also include the total number of crimes committed and the number of crimes committed within specified crime categories (i.e., crimes against persons, property crimes, drug crimes, and other crimes).

Psychosocial functioning. Data on employment, education, and family relationships over the follow-up period are collected by self-report from the CJ-DATS form. Employment variables include employment status, type of job (if employed), hours worked per month, and average monthly income over the previous six-month period. Education variables include type of education (e.g., years of education, GED, vocational training) and any diplomas or certificates obtained. Family relationship variables include living arrangements and number of days that participant had problems getting along with family and others. Psychological functioning will be measured by the composite score from the BSI. HIV-related behaviors (risky sex and drug use) will include items from the CJ-DATS form.

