Hypothesis tests are based on the assumption of group equivalence due to random assignment. However, if preliminary analysis indicates significant baseline differences, then additional control variables will be included in the analyses. Hypotheses will be tested using a two-sided .05 level of significance.

Hypotheses will initially be tested using t-tests and chi-square tests. T-tests will be used to conduct pairwise comparisons of participants in the study groups on outcomes measured as a single continuous variable. For categorical and binary outcome variables, we will use chi-square analysis. If covariates are required, analyses will be extended to ordinary least squares (OLS) or logistic regression as appropriate to the scale properties of the dependent variable. Because of missing data, inclusion of covariates, and/or repeated measures for binary outcomes, analyses may be extended to generalized linear models (McCullagh & Nelder, 1989). Structural equation modeling will be used to determine whether the effect of incentives on distal outcomes is mediated by program admission, treatment activities, admission, or retention (Kaplan, 2000).

For each hypothesis, an effect size will be calculated. The index of effect size will be the standardized mean difference (calculated as the difference between two groups divided by the pooled standard deviation); for proportions, the equivalent effect size is calculated using the arc sine transformation (Lipsey & Wilson, 2001). An effect size for study outcomes will provide a

quantitative indication of the magnitude of the difference between groups; it will also be useful in calculating power for any future study of this intervention.

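### The BSI comparison under H7 leaves out the baseline BSI unless the arms happen to differ on it, which gives up precision at almost no saving

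*Protocol*

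**What the plan says.** - **Measure.** Hypothesis Testing, paragraph on psychosocial functioning: "Psychological functioning will be measured by the composite score from the BSI". The BSI description under Psychological Status says that its nine dimensions can be combined into a Global Severity Index. Table 4 lists the BSI at both baseline and follow-up.
- **Test.** Hypothesis Testing: "T-tests will be used to conduct pairwise comparisons of participants in the study groups on outcomes measured as a single continuous variable". The text calls this the initial test and extends it to OLS if covariates are required. Significance level: "Hypotheses will be tested using a two-sided .05 level of significance".
- **When covariates enter.** Hypothesis Testing adds control variables if a preliminary analysis finds significant baseline differences. Design Analyses sets out two steps: bivariate tests between arms on selected baseline variables, then a logistic model for group membership. Variables that are significant in that model become covariates. Known association with outcome can put a variable on the list to be screened, but imbalance alone decides whether it enters.
- **Power.** Power Analysis puts the 12-month effect at "possibly around $d = 0.30$, based on a previous meta-analysis" and says that for "the follow-up interview sample in the Attendance Phase (~170), power is likely to be about .75". It remarks that covariates may help power somewhat, but names none.
- **Who has a baseline.** Recruitment - Intake Procedures says that the Attendance Phase has no baseline interview of its own. Baseline Interview Procedures, and the Baseline Interview paragraph under Data Sources, also allow baseline interviews at Walden House. The later Interview Procedures paragraph mentions only the prison.

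**The concern.** In a randomized comparison, the gain from a covariate depends on how strongly it predicts the outcome. Whether it happens to differ between arms is beside the point. A baseline measurement of the outcome itself is usually a natural candidate. Here it is collected and then left out unless it shows a significant chance imbalance, so stable differences between men in symptom level stay in the error term.

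The baseline BSI is also not one of the urn randomization factors, so its balance is left to chance. An imbalance too small to trigger the rule can still move the estimate.

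At stake is the chance of detecting a true effect on psychological functioning, in a comparison where the protocol itself expects a small effect in about 170 men.

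**Working it through.** **Inputs from the protocol.** d = 0.30 and about 170 interviewed (Power Analysis); 1:1 allocation (Randomization), so 85 per arm; two-sided .05 (Hypothesis Testing). The 170 is 85% of the Attendance Phase sample ("with retention as the outcome, the sample size of 200 will allow detection of similar effects between groups"): 0.85 × 200 = 170.

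**Input not in the protocol.** The correlation ρ between baseline and follow-up BSI composite is assumed, with .3 to .5 shown. The only related figure is that "test-retest reliability is .68 to .91 across the dimensions". That figure concerns the separate dimensions, gives no interval, and cannot stand in for a correlation over a year or more.

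**Step 1: the stated power.** For a two-sample t-test the noncentrality is d × √(n/2) = 0.30 × √(85/2) = 1.956, on 168 degrees of freedom with critical value 1.974. Power is .494 (normal approximation .498). The stated .75 is not reproduced. A one-sided test, or two-sided .10, gives .62. Using all 200 gives .56. Reaching .75 would need about 310 analysed, or d of about 0.41. The baseline for the comparison below is therefore .49.

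**Step 2: adjustment with full baseline coverage.** Regressing follow-up on arm and baseline multiplies the residual variance by 1 − ρ², so the effective standardized effect is 0.30/√(1 − ρ²), with one degree of freedom fewer.

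**Step 3: adjustment with partial coverage.** If a fraction f has a baseline BSI, the information is multiplied by about f/(1 − ρ²) + (1 − f). For an illustrative f, the protocol's introduction gives a 56% show-up rate for prison referrals. With 250 recruited in prison, 250 × .56 = 140, and 140/200 = .70. This assumes that every arrival consents and that no direct entrant has a baseline BSI.

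| Assumed ρ | Effective d, f = 1 | Power, f = 1 | Information factor, f = .70 | Power, f = .70 |
|---|---|---|---|---|
| none (unadjusted) | 0.300 | .49 | 1 | .49 |
| .3 | 0.314 | .53 | 1.069 | .52 |
| .4 | 0.327 | .56 | 1.133 | .54 |
| .5 | 0.346 | .61 | 1.233 | .58 |

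The gain is about 4 to 12 points with full coverage and about 3 to 9 points at 70%. Adjustment alone would reach .75 only at ρ of about .67 with full coverage.

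**Step 4: imbalance below the trigger.** With 85 per arm, a baseline difference is non-significant up to 1.974 × √(2/85) = 0.30 SD. At ρ = .5 such a difference moves the unadjusted estimate by 0.5 × 0.30 = 0.15 SD, half the planned effect. At ρ = .3 it moves it by 0.09 SD. These are the largest shifts that the trigger could miss, not typical ones.

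**The case against.** The strongest reply is that nothing here is invalid. An unadjusted t-test in a randomized trial is unbiased and holds its error rate, and its standard error already allows for chance imbalance. The BSI is one component of a secondary hypothesis, the t-test is described only as the initial test, and the protocol knows that covariates can help. All of this stands, and it makes the point one of efficiency. It does not remove the point, because the protocol fixes a rule for admitting covariates and that rule turns on imbalance. This is not a detail left open for a statistical analysis plan.

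A reader might also infer more than the documents support:

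- **That power would rise to .61.** That needs ρ = .5 and a baseline BSI for everyone. The protocol gives no such correlation, and its statements on who is interviewed at baseline conflict.
- **That the missing covariate explains the low power.** Most of the gap between .49 and .75 comes from sample size and effect size.
- **That every H7 outcome needs the same adjustment.** No calculation supports this. Men recruited in prison are in custody at baseline, so baseline living arrangements, and perhaps recent work or income, may predict little.
- **That the education outcome mostly records attainment from before randomization.** The protocol says "Education variables include type of education (e.g., years of education, GED, vocational training) and any diplomas or certificates obtained", but the same paragraph says that these data cover the follow-up period, so the criticism does not follow.

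**Conclusion.** The point holds for the BSI outcome under H7, as an inexpensive improvement in precision and not as a source of bias. Unadjusted power at the protocol's own inputs is .49. Adjustment for baseline BSI would bring it to between .53 and .61 with full baseline coverage, or between about .52 and .58 at 70% coverage. Both ranges rest on an assumed correlation of .3 to .5, and the 70% is illustrative. The direction of the gain does not depend on the exact value, but its size does. The stated .75 is wrong on its own inputs and needs separate correction; baseline adjustment should not be expected to close that gap.

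**What to change.** In Design Analyses and Hypothesis Testing, state that the H7 BSI outcome is analysed by regression of the follow-up composite (Global Severity Index) on arm plus the baseline composite, whether or not the arms differ at baseline. Keep participants without a baseline BSI in the analysis, through the maximum likelihood or multiple imputation already planned, or by mean imputation of the baseline value with a missing indicator.

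The cost is a change of wording, with no new data, visits or participants. The small downside is having to handle missing baselines. Stating plainly whether men who enter directly at Walden House complete the baseline BSI would show how large that task is.

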Client Evaluation of Self at Intake (CESI): Motivation Scales. This TCU form (Simpson & Joe, 1993) includes short scales for treatment motivation, psychological functioning, social functioning, and criminal thinking completed by the client. This study will use the motivation scales, but will modify the readiness for treatment subscale to refer specifically to aftercare. The motivation scales correspond to the Stages of Change model as delineated by Prochaska and DiClemente (1986). The self-assessment of drug use ($\alpha=.91$) scale consists of nine items that are intended to differentiate between those who have begun the contemplation stage and those who remain in the precontemplation stage. The desire for help ($\alpha=.83$) scale consists of seven items assessing the transition from general acknowledgment of a drug problem to recognition of the need for help. Finally, the readiness for treatment ($\alpha=.63$) scale has eight items intended to assess willingness to enter and comply with treatment, and represents the completion of the above transition and the beginning of the action stage.

Counseling Utilization Form. Once a week, the research assistant will check each participant's clinical records and note how many treatment sessions (individual or group) were scheduled for the participant and how many the participant attended.

CM Record Form. In order to check on protocol adherence and to collect data for analysis, this form provides a record of information about attendance, date of the receipt of the voucher, amount of the voucher, and items redeemed.

Treatment Termination Form. This short form records whether a participant completed the intervention and, if relevant, the reason for early termination (e.g., incarceration, transfer to another program, voluntary withdrawal from study and reasons for doing so). (Note that except for participants who request to be removed from the study, all randomized subjects will be tracked for follow-up.)

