Although the validity of self-report by clients of their behavior is often in question, prior research indicates that self-report interviews, when properly conducted, are generally reliable and valid in measuring drug and alcohol use (Buchan, Dennis, Tims, & Diamond, 2002; Chou, Hser, & Anglin, 1996; Darke, 1998) and criminal involvement (Elliot, Huizinga, & Ageton, 1982; Junger-Tas & Marshall, 1999; Thornberry & Krohn, 2000). Biological-based data increases the credibility of findings from self-report, but such data cannot reveal distant use or long-term patterns of use, nor can criminal justice records verify criminal behavior that does not come to official attention. Still, policy makers prefer objective measures of criminal justice involvement to self-reported measures. For the proposed study, we will use several procedures to increase the reliability and validity of self-report data. First, interviewers will assure participants that information that they provide as part of research will not be revealed to parole or other agencies, will not become part of their parole or treatment records, and is protected by a certificate of confidentiality. Second, interviewers will inform participants at the start of the follow-up interview that they will be asked to provide a urine specimen after the interview that will be tested for illicit drugs. Third, with respect to criminal justice system involvement, we will obtain official arrest and incarceration records from the California Department of Justice and the California Department of Corrections and Rehabilitation, which can be used to verify self-reported arrest and incarceration.

HYPOTHESIS TESTING

For the Admission Phase, the independent variables are Admission Incentive vs. Admission Comparison. For the Attendance Phase, the independent variables are Attendance Incentive vs. Attendance Comparison.

Primary dependent variables will be the proximal outcomes of treatment admission and retention. Secondary dependent variables will be the distal outcomes of substance use, crime, and psychosocial functioning, including employment, education, family relationships, psychological functioning, and HIV risk.

Treatment admission. Whether study participants completed intake for admission to the Walden House residential program and the outpatient program will be based data from program records. Time to admission, calculated from date of parole release to date of enrollment, will also be examined.

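### The planned mediation model lets a custody event during the stay both count as the crime outcome and shorten retention, which biases the retention-to-crime path toward apparent benefit

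*Protocol*

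**What the plan says.** All of the relevant definitions are in the protocol.

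- **Model.** Hypothesis Testing commits to the analysis: "Structural equation modeling will be used to determine whether the effect of incentives on distal outcomes is mediated by program admission, treatment activities, admission, or"; the last mediator in that list is retention.
- **Outcome family.** The same section states: "Secondary dependent variables will be the distal outcomes of substance use, crime, and psychosocial functioning".
- **Crime window.** Under Criminal justice involvement and criminal activity, rearrests, reincarcerations and dispositions from state records are counted "over the 18-month period following release to parole (covering the six-month intervention period and the 12-month follow-up period"). They are also coded as binary: "any arrest during the specified period vs. none, reincarceration vs. none".
- **Mediator.** Under Treatment retention, the continuous version is "measured as the number of days of attendance at Walden House (up to a maximum of 26 weeks or 180 days"). The binary version, completion, is "attending the Walden House program for 26 weeks or leaving under favorable circumstances"; the examples of favorable circumstances do not include custody.
- **Link between them.** The Treatment Termination Form (Data Sources, Treatment) records "the reason for early termination (e.g., incarceration, transfer to another program" and other reasons.

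The mediation model is given no lag, no landmark and no rule for events that end the stay. Event dates will be held, but the only stated use is time to rearrest or reincarceration. The Cox regression under Other Analyses is a separate analysis and does not place retention before crime.

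**The concern.** A mediation model needs the mediator to come before the outcome. Here the two overlap: retention accrues during roughly the first third of the crime window. A man taken into custody on day 40 has a short stay because of the event, and he is also counted as a recidivist because of it. The model reads this as a short stay going with crime.

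The trial's rationale is that incentives raise exposure to treatment and that exposure improves long-term outcomes. This model is the planned test of the second link. The protocol also notes that policy makers prefer objective criminal justice measures, and those are the outcomes affected. A spurious result would be read as evidence that paying for longer stays reduces recidivism.

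**Working it through.** **1. Overlap of the windows.** 6 months + 12 months = 18 months, as the protocol states. Retention accrues over 180 days, about 6/18 = one third of that window.

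**2. Inputs.**
- Attendance Phase sample of 200, 100 per arm assumed; two-sided 0.05 (Power Analysis, Hypothesis Testing).
- Mean dropout time, assumed: 38 vs 57 days or 75 vs 115 days. The 38 is the site's average attendance (Conception of the Problem). The longer pair is near the 64- and 80-day stays reported for the earlier case-management study (Preliminary Studies).
- 12-month event rate, assumed 29% to 50%. The 29% is the return-to-custody figure in the prison treatment evaluations. The 50% is guided by the Drug Use and Crime section, which gives 50% or more returning to drug use and crime within a year.
- Share of in-stay events that end the stay, not given: 100% and 50%.
- Retention has no effect on crime, by construction. Both clocks start on the same day.

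**3. Why the path is biased.** Take a constant event rate λ = −ln(1 − p)/365, which is 0.000938 per day at 29% and 0.001899 at 50%. Count events to day 540 and let every in-stay event end the stay.

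A man with a full 180-day stay was event-free to day 180, so his risk is 1 − exp(−360λ):
- 29%: 1 − exp(−0.338) = 29%
- 50%: 1 − exp(−0.684) = 50%

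A man whose stay ended on day 30 (mean dropout 75 days) left because of an event with probability f = λ/(λ + 1/75). Otherwise he has 510 days still at risk. His risk is f + (1 − f)(1 − exp(−510λ)):
- 29%: 0.066 + 0.934 × 0.380 = 42%
- 50%: 0.125 + 0.875 × 0.620 = 67%

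Longer stays thus appear to cut risk from 42% to 29%, or from 67% to 50%, although retention does nothing.

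**4. How often this gives a false finding.** Null simulation with mediator = min(dropout, stay-ending event, 180). Path a is arm to days attended. Path b is days attended to any event by day 540, adjusted for arm, by logistic regression. Mediation is declared when both paths are significant.

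| Setting | Path b significant | Mediation declared |
|---|---|---|
| As written, every in-stay event ends the stay | 10–36% (favorable direction; nominal 2.5%) | 8–22% |
| As written, half of in-stay events end the stay | 6–12% (favorable direction) | 4–8% |
| Events counted after day 180 among men event-free then | 4–6% (two-sided) | 3–4% |

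The lower ends belong to 38 vs 57 days and the upper ends to 75 vs 115 days.

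**5. What the result depends on.** A second set of null runs used linear models, stays of 110 vs 172 days and an 18-month arrest risk of 50%. Mediation was declared in 28.5% of runs when every in-stay arrest ended the stay, 10.5% when half did and 3.8% when none did. With 110 days in both arms, path b was still falsely significant in 37%, but mediation was declared in only 2%.

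**The case against.** **The protocol gives this model one sentence.** It does not say which crime variable enters, and self-reported crime over the six months before follow-up is also available. Such detail is often left to an analysis plan. This narrows the point to the records-based outcomes but does not remove it. The protocol itself fixes the retention window, the records window and the use of retention as mediator, and those definitions applied together produce the bias.

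**Not every arrest ends a stay.** Incarceration is only an example on the form, the voucher rules allow discharge and readmission within the 22 weeks, and retention is days attended, not time to first exit. This stands, and it is why the 50% row is given beside the 100% row.

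**The consequence is limited.** None of H1–H9 is a mediation hypothesis, and intent-to-treat is the main approach. This also stands.

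**A lag does not make the estimate causal.** With unmeasured variation in arrest risk added to the second set of runs (gamma, variance 1), counting only later arrests still gave a significant path in 12% and mediation in 7.5%. Those runs kept men with an earlier arrest. Restricting to event-free men closes that route, but not a trait that drives both voluntary leaving and arrest.

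A reader might infer that retention will look like a mediator in most trials. The documents do not support that: only the direction of the bias in path b is certain when custody ends stays, and significance depends on the assumptions above. Much larger rates arise if the arrest rate is assumed to double during treatment, but no figure in the protocol supports doubling.

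**Conclusion.** The point holds for one analysis: retention as mediator of records-based rearrest and reincarceration over 18 months from release. As defined, the path from retention to crime is biased toward benefit whenever custody ends stays, and false mediation can be inflated when incentives raise retention, which is the trial's own H3. With 200 men and the assumed stays and event rates, the rate is about 8–22% if every in-stay event ends the stay and about 4–8% if half do, against about 3–4% with a lagged outcome. At the site's 38-day average stay the inflation is at the low end.

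It would be wrong to extend this to all distal outcomes or to the trial's main conclusions. Self-reported crime over the six months before follow-up and the other late-measured outcomes are not affected. The intent-to-treat comparison of arms for H6 is also valid over the full 18 months, because it does not condition on retention. The protocol gives the intervention as five months or 22 weeks in some places and six months in others, but a crime window that starts at release includes the treatment period under any of these.

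**What to change.** For the mediation model of records-based crime only:

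1. Count events from the point where the retention window closes, among men event-free at that point. Under the current definition this is day 180; if the intervention length is reconciled across sections, use the reconciled length. Set the point on the retention clock, because admission can follow release by up to two weeks. Alternatively, use Cox regression with retention to date as a time-dependent covariate.
2. Adjust the retention-to-outcome path for baseline Lifestyle Criminality Screening Form risk, motivation and drug-use severity, all already collected.
3. Report the result as associational, since unmeasured shared causes of leaving and arrest remain.

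Leave the 18-month intent-to-treat analysis of H6 unchanged.

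The cost is analysis wording, as event dates are already to be obtained. With the landmark, the price is fewer events and a population selected on being event-free after randomization, which should be stated with the result.
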